16.0 Withdrawal of Subjects

16.1 Describe circumstances under which you anticipate subjects could be withdrawn from the research without their consent:

Participants may be withdrawn from the research without their consent if they become ineligible based on inclusion/exclusion criteria or learning of a contraindication for continuing, they demonstrate inconsistent delay discounting rates at the baseline session, there is an emergency, and/or they are not adherent with ARRC policies.

16.2 If applicable, describe any procedures for orderly termination (e.g., discontinuation of a study drug or debriefing after a behavioral intervention):

If a participant is withdrawn from the study, he or she will be informed that we have collected all the data required from their participation. If a participant is withdrawn or voluntarily discontinue, their compensation for the study will be pro-rated accordingly.

16.3 Describe procedures that you will follow when subjects withdraw from the research, including partial withdrawal from procedures with continued data collection (e.g., participant declines to continue with regular blood draws, but continues with periodic behavioral questionnaires):

If a participant is withdrawn or discontinued, they will be withdrawn from the entire study.

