counterbalanced to either the active or control group based on alcohol use (e.g., average drinks per day) and their baseline delay discounting rate. Both groups will be exposed to the same procedures. That is, participants in both groups will generate positive cues at either future timepoints (active, Episodic Future Thinking, EFT) or recent timepoints (control, Control Episodic Thinking, CET). Following this Session 3, participants will begin the first intervention period (Monitoring Part 1). The intervention period will last approximately 14 consecutive days, with three breathalyzer screens per day. During this 14-day period, participants will also self-report their previous-day alcohol use daily remotely and their alcohol withdrawal symptoms per day. Following Monitoring Part 1, participants will return to the laboratory for Session 4, where they will generate new cues and complete assessments. Following Session 4, participants will begin the second intervention period (Monitoring Part 2). The intervention period will last approximately 14 days, with three breathalyzer screens per day. During this second 14-day period, participants will self-report their previous-day alcohol use remotely. Session 5 will be conducted in the laboratory after the conclusion of Monitoring Part 2. Participants will also complete Session 6 (1-month follow-up) one month after the conclusion of the intervention. Participants may be provided a cell phone (if necessary) at the beginning of the study and a BACtrack breathalyzer at the beginning of the baseline period.

Participants may receive a \$100 study completion bonus at the end of the study provided they complete all six sessions (and return the cell phone if applicable). Please note: if participants are unable to complete the entire 28-day intervention period, post-intervention data will be collected regardless of the number of intervention days completed.

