12.0 Inclusion and Exclusion Criteria

12.1 Describe how you will screen individuals for eligibility. When will screening occur and what procedures will you use? Upload any screening scripts or surveys to Protocol Management:

We have developed and are currently using a separate pre-screening survey (online/phone pre-screen), which occurs prior to enrolling participants into our intervention protocols.

This pre-screening ensures that participants are likely to meet all inclusion/exclusion criteria (e.g., MRI scanner eligibility) prior to enrolling into any randomized study. This initial pre-screening (online/phone) may be completed online or over the phone. Information is stored in REDCap, which is HIPAA compliant and password protected. If participants seem eligible from the online/phone screen, they will be scheduled for the in-lab screen in the laboratory to further determine eligibility and appropriateness for this specific intervention-based study.

12.2 Describe the eligibility criteria that define who will be included and who will be excluded from enrollment for each procedure of your study.

Include any geographic criteria (e.g., Virginia Tech undergraduate students, a national sample of adults with engineering degrees, minors aged 8-12 in the New River Valley, university faculty in Virginia and Paris, France):

Inclusion criteria for signing consent will require that participants: (1) demonstrate high-risk or harmful drinking (AUDIT>15; i.e., 16 or higher), (2) be between 21-65 years old, and (3) have a desire to quit or cut down on their drinking, but do not have proximate plans to enroll in treatment for AUD during the study period.

Exclusion criteria include: (1) meeting moderate to severe DSM-5 criteria for substance-use disorders other than alcohol, nicotine, or marijuana, (2) having a current diagnosis of any psychotic disorder, (3) having a history of seizure disorders or traumatic brain injury they have not fully recovered from, (4) having any contraindication for participation in the fMRI session, or (5) reporting current pregnancy or lactation.

12.3 Indicate specifically whether you will include or exclude each of the following special populations: (You may not include members of these populations as subjects in your research unless you indicate them in the description of your subject population.)

- *Minors, as defined by state law where the study is performed (infants, children, teenagers)*

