Participants will be screened, using medical history and structured interviews, for a history of medical contraindications (e.g., recent myocardial infarction, current pregnancy), current unstable medical illness, and psychiatric disorders (including other substance use disorders). The studies will be conducted at FBRI. Participants will be free to withdraw from the study at any time, and their refusal to continue will not affect other medical care. In addition, if participants develop medical problems during the course of the study, assessments to determine whether participants should continue will be conducted by the Study Physician and necessary referrals will be provided. The risks enumerated above will be addressed by the following protections against risk, and reviewed by the Data and Safety Monitoring Board:

1. Adverse emotional reactions: [name] will monitor participants' adverse emotional reactions.
2. Alcohol withdrawal: In addition, participants who are not drinking alcohol may experience alcohol withdrawal symptoms during any of the laboratory sessions or if they are drinking less than they normally do during the proof-of-concept field study portion of this study. At each laboratory session, participants will complete the Alcohol Withdrawal Symptom Checklist (AWSC), a validated 17-item checklist of symptoms in which the

participant rates their experience from 0 (“Not at all”) to 4 (“Extreme”). A score of >23 on this checklist requires medical oversight for alcohol withdrawal and will trigger the research staff to contact [name]. [name] will speak with the participant to determine appropriateness and safety to continue in the study and to provide medical consultation and/or a referral to a clinic/primary care physician. If the participant produces a score of >23 on the checklist, [name] will be contacted to assess the participant’s risk and refer as necessary. We have successfully implemented these procedures with [name] in our previous and ongoing studies.

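### Protocol Sections 16.3 and 8.2 give conflicting rules on collecting data after a randomised participant stops early, so Session 5 and 6 outcomes may be lost for reasons related to response

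*Protocol*

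**What the plan says.** Three places in the Protocol bear on someone who stops early.

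- **Section 16.3**: "If a participant is withdrawn or discontinued, they will be withdrawn from the entire study". The template question above this answer asks about people who give up some procedures but go on supplying data. The answer leaves no such category.
- **Section 16.2**: a withdrawn participant is told that collection is over: "he or she will be informed that we have collected all the data required from their participation".
- **Section 8.2**: "if participants are unable to complete the entire 28-day intervention period, post-intervention data will be collected regardless of the number of intervention days completed".

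Section 16.1 lists grounds on which staff may withdraw someone without consent, among them "if they become ineligible based on inclusion/exclusion criteria or learning of a contraindication for continuing". The wording is permissive and does not say whether this ground stops at randomisation. Section 17.2 provides that when the Alcohol Withdrawal Symptom Checklist (AWSC) score exceeds 23, a medical contact "will speak with the participant to determine appropriateness and safety to continue in the study" and gives consultation and/or a referral. Section 14.4 expects everyone to attend all sessions unless they withdraw.

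The SAP (Statistical Analyses, Objective 1) treats missed assessments as missing. If missingness is high, it allows last observation carried forward or a worst-case rule. Its Sensitivity Analyses compare attrition between arms and look for predictors of drop-out. It does not say whether a participant who stops the intervention is still followed.

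**The concern.** For the same person, one section tells staff to collect the post-intervention data and another tells them to end participation. What happens then depends on which label a staff member applies.

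At stake is the comparison of the arms after the intervention. Discounting is the primary measure of the temporal window, and demand and craving are also named endpoints. Someone removed before Session 5 has no post-intervention value for any of them.

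The loss need not be random. The trial's hypothesis is that EFT reduces drinking. Section 17.2 recognises that participants who drink less than usual in the field period may have withdrawal symptoms, and symptoms can lead to a decision on continuing. At least one documented exit can therefore follow from response, and it may occur unequally between arms if EFT works. The AWSC is itself a secondary outcome in the SAP, so losing people who were stopped after a high score would also truncate that outcome.

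**Working it through.** The plan states no figure on this point, so there is none to reproduce. The check sets the rules side by side and then asks what is lost, why, and for how many.

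**1. Who falls under which rule**

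| Situation after randomisation | Section 8.2 | Section 16.3 |
|---|---|---|
| Intervention cut short, but nobody records a withdrawal or discontinuation | Data collected | Not triggered |
| Participant stops the cues, or staff stop them, and this is recorded as discontinuation | Data collected | Leaves the entire study |
| Participant withdraws consent | Not addressed | Leaves the entire study |

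The second row is the conflict. No section defines *discontinued* or *unable to complete*, so nothing decides between the first and second rows.

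**2. What is lost if 16.3 is applied**

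Inputs: 28 intervention days, one drinking report and three breath samples a day, Session 4 after day 14, and Sessions 5 and 6 afterwards (Sections 8.1 and 8.2). Section 8.2 places the questionnaires and tasks in Sessions 2 to 6 without a schedule by measure. I take discounting, demand and craving to be session-based; Section 17.2 puts the AWSC at every laboratory session.

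- Stopped on day 10 (an illustrative day): 28 − 10 = 18 drinking reports, 18 × 3 = 54 breath samples, and Sessions 4, 5 and 6.
- Stopped at Session 4: 14 drinking reports, 14 × 3 = 42 breath samples, and Sessions 5 and 6.
- Stopped at Session 5: the daily data are complete; mainly Session 6 is lost.

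Nothing says that data collected before exit are discarded.

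**3. Whether exit can depend on response**

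Section 17.2 supplies each link: drinking less may bring symptoms, an AWSC score above 23 triggers medical contact, and that contact includes a judgement on continuing. The same section has the Study Physician assess whether participants who develop medical problems should continue. The result is a possible stop, not an automatic one.

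**4. How many could be affected**

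Non-completers = number entering × (1 − retention), at the stated rates.

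- Protocol Section 14.1: 200 × 0.80 = 160 randomised; 160 × 0.65 = 104 completers; 160 − 104 = 56 non-completers (35%).
- SAP, Recruitment and Participant Retention: 170 × 0.75 = 127.5 continuing after baseline; 127.5 × 0.30 = 38.25, about 38 non-completers (30%).

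These are totals for every kind of loss. The share withdrawn or discontinued, rather than simply lost to contact, is not given. On these rates the number affected lies between 0 and about 56 (Protocol) or 0 and about 38 (SAP).

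**5. What the analysis can do about it**

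The attrition comparisons can show that loss differs by arm or by measured characteristics. They do not restore a missing Session 5 value, and they do not call for the reason for exit. If the worst-case rule were used for breath samples, someone stopped because of symptoms after cutting down would be counted as positive on every missing sample.

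**The case against.** The strongest reply is that the rules apply to different people. Section 8.2 covers someone still in the study whose intervention was shortened, Section 16.3 covers someone who has left, and Section 14.4 fits both. This reading is coherent, and it means that an outright contradiction is not proved. But the text does not state it, and it does not help with a participant whom staff stop during the 28 days. The undefined terms remain a defect.

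The AWSC route is also narrow. The checklist is given at laboratory sessions, and Session 4 is the only one inside the 28 days. That limits the likely number without removing the route. The SAP's attrition and missing-data plans likewise reduce the problem only in part.

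A reader might infer four stronger things that the documents do not support.

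- **Starting treatment, or an AUDIT score falling below 16, leads to removal.** Neither is named as a ground. The criterion that participants "do not have proximate plans to enroll in treatment for AUD during the study period" is set for signing consent and concerns plans; the AUDIT threshold is likewise set at consent. The SAP compares AUDIT scores between arms, which sits poorly with removing people whose score falls. Section 16.1 says only that participants may be withdrawn, and one neighbouring ground refers to the baseline session.
- **Removed participants lose safety follow-up.** In-study symptom reports would end, but Section 17.2 provides consultation and/or referral, and Section 21.1 defers monitoring to an attached plan that is not among the documents reviewed. Absence of later follow-up cannot be shown.
- **The bias can be put at 22% to 39% of a 0.5 SD effect.** That follows if the top 5% or 10% of EFT responders are removed and nobody in CET is: 0.1031/0.95 = 0.109 SD, or 0.1755/0.90 = 0.195 SD. No document supports those shares. No removal in CET is implausible when both arms must want to quit or cut down. The calculation also ignores daily data kept before exit, which the mixed model of drinks can use.
- **The whole 30% to 35% loss comes from Section 16.3.** That figure is total attrition.

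**Conclusion.** The concern holds as a conflict of rules with a real consequence for the data. As written, Section 16.3 excludes continued data collection, Section 8.2 requires it, and undefined terms let both apply to a randomised participant who stops during the intervention. Following 16.3 loses the Session 5 and 6 outcomes and the remaining daily reports, and the Protocol itself describes one route by which such an exit could follow from drinking less.

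The size of any bias cannot be estimated. It depends on the share of the expected 30% to 35% loss that is withdrawal or discontinuation, on how strongly those exits relate to response, and on whether they differ between arms; the documents give none of these. The conclusion assumes that discounting, demand and craving are collected only at sessions and that staff would apply 16.3 literally. The effect is likely to be greater on the session-based outcomes than on daily drinking, where data before exit still contribute.

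**What to change.** - Reconcile Section 16.3, and the statement to participants in 16.2, with Section 8.2 by defining stopping the intervention separately from leaving the study.
- State that a randomised participant who stops the intervention remains in outcome data collection (daily reports, Sessions 5 and 6) unless they withdraw consent or the responsible clinician judges a procedure unsuitable. Say which outcome and symptom data are collected in each case, and carry the same wording into the SAP.
- Record the date and reason for every exit, and add reason for exit to the SAP's attrition analyses.
- Clarify whether the ineligibility ground in Section 16.1 applies after randomisation, and reconcile it with Sections 12.2 and 17.2. Which clinical grounds should lead to stopping is for the investigators and the Study Physician; this point proposes no such rule.

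The cost is an amendment to the wording, a line in the consent form, and the existing session and report payments for those retained. Outcome data not collected at the time largely cannot be recovered later.

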17.0 Risks to Subjects

17.1 List the reasonably foreseeable risks, discomforts, hazards, or inconveniences to the subjects related to the subjects' participation in the research. Include for the IRB's consideration a description of the probability, magnitude, duration, and reversibility of the risks. Consider physical, psychological, social, legal, privacy, and economic risks. Do not indicate "No risk" or "N/A." Instead, for studies with very low risk (e.g., anonymous online questionnaire on a mundane topic) indicate "The investigators are not aware of any risks from participation in this study." or "No more than risks than are found in everyday life." The example consent form presents a tabular method for risk information, which you can also use here. Common risk types include:

- *Physical (e.g., potential for pain, discomfort, infection)*
- *Psychological (e.g., potential for stress, discomfort, and/or embarrassment)*
- *Social (e.g., potential for discrimination or stigmatization and disruption of personal and family relationships)*
- *Legal (e.g., potential for disclosure of illegal activity, negligence)*
- *Privacy (e.g., potential for personal information being accessed, used, or disclosed without the subjects' knowledge or consent, breach of confidentiality/security)*
- *Economic (e.g., potential for individuals to lose access to economic services, employment, insurability)*

There are minimal risks involved in participation, including:

1. Adverse emotional reactions: These reactions may be related to changes in drinking, or to some of the research tasks. Participants may also feel uncomfortable disclosing personal information such as drug use history.
2. Alcohol withdrawal: At sessions not including alcohol, participants may experience alcohol withdrawal symptoms such as shaking, sweating, or chills.
3. Loss of confidentiality: The research team will employ every effort to maintain participant confidentiality, however the loss of confidentiality is a potential risk, specifically associated with the collection, storage, and transmission of data via an app.
4. Incidental findings: Incidental findings including positive pregnancy tests and possible neuroimaging abnormalities may occur.

17.2 Indicate the measures you will use to minimize risks and monitor subjects for safety. (e.g., asking a subject at regular intervals to rate how they are feeling from 1 to 10, or to slowly crouch in order to check their balance.)

Informed Consent. All consenting methods will be conducted using standard operating procedures, and all staff (including recruitment staff) will be provided with human subjects protection training as well as cultural sensitivity training. All participants will enroll on a voluntary basis and sign an IRB-approved consent form prior to study participation.

Participants will be provided with a copy of the consent form following phone or online screening by email or mail when possible. To accommodate "walk-in" study screens and/or participants unable to receive email or physical mail (e.g., "homeless" without physical address, email address, or access to a computer), we will provide a hard copy of

the consent form to review. In all cases, participants will be given as much time as needed to review the consent and ask any questions. Participants will also be informed that they may choose to take the consent with them and return at a later date to enroll into the study. During the consent process, participants will be given adequate time in a quiet room to read (or further review) the written consent form.

Research staff will review each element of the written consent form with the potential participant. The potential participant will be given the opportunity to ask questions and will have as much time as they need to decide whether they would like to participate in the study. Staff will reiterate that the potential participant can choose to decline participation in the study at that time or at any time thereafter without consequence. The potential participant and person obtaining consent will sign the consent form after the potential participant verbally states that they understand the conditions of the study, have no more questions, and chooses to participate. In addition, an Evaluation to Consent will be administered to ensure participants have a good understanding of the study. Participants unable to provide informed consent for themselves will not be eligible.

Participants will be informed that the breathalyzer provided to them in this study should not be used as a tool to determine whether research participants should operate a motor vehicle or other equipment, or perform any other dangerous act. The participants will be informed, verbally and in the informed consent document, that the results of any study breath samples using the study provided breathalyzer cannot be used in court.

Protections Against Risk:

Participants will be screened, using medical history and structured interviews, for a history of medical contraindications (e.g., recent myocardial infarction, current pregnancy), current unstable medical illness, and psychiatric disorders (including other substance use disorders). The studies will be conducted at FBRI. Participants will be free to withdraw from the study at any time, and their refusal to continue will not affect other medical care. In addition, if participants develop medical problems during the course of the study, assessments to determine whether participants should continue will be conducted by the Study Physician and necessary referrals will be provided. The risks enumerated above will be addressed by the following protections against risk, and reviewed by the Data and Safety Monitoring Board:

1. Adverse emotional reactions: [name] will monitor participants' adverse emotional reactions.
2. Alcohol withdrawal: In addition, participants who are not drinking alcohol may experience alcohol withdrawal symptoms during any of the laboratory sessions or if they are drinking less than they normally do during the proof-of-concept field study portion of this study. At each laboratory session, participants will complete the Alcohol Withdrawal Symptom Checklist (AWSC), a validated 17-item checklist of symptoms in which the

participant rates their experience from 0 (“Not at all”) to 4 (“Extreme”). A score of >23 on this checklist requires medical oversight for alcohol withdrawal and will trigger the research staff to contact [name]. [name] will speak with the participant to determine appropriateness and safety to continue in the study and to provide medical consultation and/or a referral to a clinic/primary care physician. If the participant produces a score of >23 on the checklist, [name] will be contacted to assess the participant’s risk and refer as necessary. We have successfully implemented these procedures with [name] in our previous and ongoing studies.

3. Loss of confidentiality: The use of ID numbers for participants, and keeping all data in a locked cabinet in locked offices, will protect confidentiality. Password protected computer databases will have coded identifiers, and a Certificate of Confidentiality will be obtained. Master files linking subject names to study ID numbers will be kept separate from the data. These screening, monitoring, and confidentiality procedures have been in effect for decades and for thousands of participants across the various protocols employed by our group across various institutions. Although there is a potential risk to confidentiality, there are actions taken to reduce the risk to confidentiality via collection of data through an app. First, all transmissions from the breathalyzer to the phone and from the phone to University of Kentucky are encrypted and secured. The RAM app is HIPAA compliant. Additionally, servers are password protected and located behind firewalls to minimize the risk to confidentiality.

4. Incidental findings: In the event of an incidental positive pregnancy test finding, the study personnel will share the results with the participant, and will counsel the participant as to what clinical referral might be appropriate. . Incidental findings are an important factor in the risk/benefit analysis of neuroimaging studies. The Human Neuroimaging Lab at Virginia Tech has a standardized approach to incidental findings across approximately 60 currently active protocols (including scanning over 150 individuals with AUD) approved by two separate IRBs (Virginia Tech and Carilion Clinic). Moreover, our process is consistent with the best practices recommendations of the NIMH “MRI Research Safety and Ethics: Points to Consider” whitepaper (https://www.nimh.nih.gov/about/advisory-boards-and-groups/namhc/reports/mri-research-safety-ethics_33826.pdf). Furthermore, our procedures conform with those reported in the literature as appropriate for our research setting. During the consenting process, participants are informed that the scans that will be performed in the study are not the same as those that would be used in a clinical setting, and thus have limited diagnostic value. Further, some of the scans require subsequent data analysis and would never be read by a neuroradiologist. As is common and acceptable in many academic institutions, we do not have a neuroradiologist on staff to read every scan. Our policy (which is communicated to all participants verbally and written in the consent document):

"This is not a study to diagnose these structures. Your brain images will not be read by a doctor who specializes in reading brain images. If something abnormal is observed by chance, we will tell you. You will then be counseled as to what clinical referral would be appropriate. We are not qualified to make any diagnosis, nor is this fMRI of diagnostic

quality for medical purposes. In the event of an incidental positive pregnancy test finding, the study personnel will share the results with you. They will counsel you as to what clinical referral might be appropriate "

We also communicate, however, that we will err on the side of caution in communicating with them if we do observe a possible abnormality. Finally, we will institute a DSMB that includes a radiologist and will, on a semi-annual basis, review our process for recognizing and reporting incidental findings in this project.

17.3 If applicable, indicate which procedures might have risks to the subjects that are currently unforeseeable. This will be rare, and usually applicable when testing a new drug or device or a new use of an existing drug or device:

N/A

17.4 If applicable, indicate which procedures might have risks to an embryo or fetus should the subject be or become pregnant:

N/A

17.5 If applicable, describe risks to others who are not subjects (e.g., collection of sensitive health data that might affect sexual partners if disclosed, mandatory reporting of abuse, DNA testing that might affect family members or relationships):

N/A

